3.3 Study Duration, Enrollment, and Number of Subjects

Study duration for each participant will last less than 8 weeks (enrollment during initial hospitalization through postpartum visit). 160 patients will be enrolled. This is anticipated to take approximately 18 months.

3.4 Study Population

English and Spanish-speaking postpartum women, who delivered at or beyond 20 weeks' gestation, with a diagnosis of chronic hypertension, gestational hypertension, or preeclampsia requiring initiation of antihypertensives.

Exclusion criteria: Use of antihypertensives antepartum, allergy to nifedipine or amlodipine, persistent tachycardia (as defined by treatment team).

4 STUDY PROCEDURES

[figure not shown]
4.1 Screening procedure

Women will initially be screened for study participation at the time of admission to Greenville Memorial Hospital's Family Birthplace unit. Additionally, women who do not initially meet criteria will be rescreened daily for the development of a new hypertension diagnosis. Women will be consented for enrollment and randomized at the time of admission or at time of diagnosis to ensure maximum trial participation. Not all women who are initially consented will meet criteria for final inclusion in the study and initiation of the study drug. Based on review of historical data, approximately 50% of patients who meet diagnostic criteria will eventually meet criteria for medication administration.

4.2 Intervention

Once a woman meets inclusion criteria for antihypertensives, she will be administered the appropriate study drug. Randomization will have already occurred at the time of enrollment so that there will not be a delay in patient treatment while awaiting randomization. Randomization

will not be blinded. Women in group 1 will be started on amlodipine 2.5 mg daily and women in group 2 will be started on nifedipine ER 30 mg daily. Aside from the study drug assignment, the remainder of the patient's postpartum care will be performed according to the clinical team's discretion. Study flow is described in the below figure.

4.3 Subject Completion/Withdrawal procedures

Participants are instructed to inform their enrolling research personnel if they desire to withdraw from the study, at which point participation will be terminated.

5 STUDY EVALUATIONS AND MEASUREMENTS

-Demographic characteristics and clinical data will be abstracted from the medical chart

-Maternal age

-Gestational age at delivery

-Race

-BMI

-Parity

-Mode of delivery

-Hypertensive diagnosis

-History of diabetes (gestational or pre-gestational)

-Length of stay from delivery until discharge

-Number of acute antihypertensive treatments

-Number of dose increases of initial study drug

-Number of additional long-acting antihypertensives started

-Magnesium use

-Side effects reported

-Medication discontinuation

-Discharging physician

-Blood pressure at blood pressure check appointment

-Blood pressure at postpartum visit

- Readmissions from time of discharge until postpartum visit
- Breastfeeding status at time of postpartum visit
- Patient-reported length of breastfeeding
- Patient-reported breastfeeding satisfaction

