PROTOCOL TITLE: Amlodipine versus nifedipine ER for the management of postpartum hypertension: A randomized controlled noninferiority trial

Lead Investigator:

[name]

Prisma Health/University of South Carolina Greenville

Version Date: August 8, 2022

TABLE OF CONTENTS

Table of contents.....	2
Protocol Synopsis.....	3
1 BACKGROUND AND RATIONALE.....	5
2 STUDY OBJECTIVES.....	7
3 INVESTIGATIONAL PLAN.....	8
4 STUDY PROCEDURES.....	9
5 STUDY EVALUATIONS AND MEASUREMENTS.....	12
6 STATISTICAL CONSIDERATIONS.....	13
7 DATA COLLECTION AND MANAGEMENT.....	13
8 REFERENCES.....	13

PROTOCOL SYNOPSIS

Study Title	Amlodipine versus nifedipine ER for the management of postpartum hypertension: A randomized controlled noninferiority trial
Funder	Prisma Health OBGYN Departmental Research Fund
Study Rationale	
-A significant number of pregnancies are complicated by hypertensive disorders (chronic hypertension, gestational hypertension, preeclampsia)-Hypertension is often exacerbated in the postpartum period-Many of these patients require initiation of antihypertensives after delivery-There are a limited number of well-studied treatment options routinely used (labetalol and nifedipine ER)-Prior studies have shown that both labetalol and nifedipine ER are effective-Nifedipine ER has few contraindications, but has significantly more side effects than labetalol-Headache is one of the most commonly reported side effects with nifedipine ER-Headache is also a commonly reported symptom of preeclampsia-Amlodipine is in the same drug class as nifedipine ER, but does not cause headaches-Amlodipine is a first-line antihypertensive in the non-obstetric population-Amlodipine has not been studied in the obstetric population
Study Objectives	
Primary
 
-To evaluate whether amlodipine is noninferior to nifedipine ER in the management of postpartum hypertension 
Secondary
 
-To evaluate whether patients tolerate amlodipine better than nifedipine ER
Study Design	Unmasked, pragmatic randomized controlled trial

Subject Population Inclusion criteria

- English and Spanish-speaking postpartum women with a diagnosis of chronic hypertension, gestational hypertension, or preeclampsia
- Delivery at or beyond 20 weeks' gestation

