1 BACKGROUND AND RATIONALE

Hypertensive disorders of pregnancy are a major cause of maternal morbidity and mortality, and it is felt that at least a portion of these adverse outcomes are preventable¹. Worldwide, between 2 and 8 percent of pregnancies are complicated by preeclampsia². Additionally, 0.9 to 1.5 percent of pregnant women have pre-existing chronic hypertension³. Postpartum hypertension can either be due to an exacerbation of existing chronic hypertension or preeclampsia, or it can be new onset^{2,4}. Blood pressures tend to increase in the postpartum period, peaking at three to six days postpartum. It is not uncommon for women who did not require medications during the pregnancy to be started on an antihypertensive in the postpartum period^{3,5}. If blood pressures are greater than or equal to 150 mmHg systolic and/or 100 mmHg diastolic on two occasions four to six hours apart, antihypertensive therapy is recommended^{4,6,7}.

The most commonly used antihypertensive medications in the postpartum period are labetalol and nifedipine ER. Studies have shown that nifedipine ER is at least as effective, and potentially even more effective, than labetalol in achieving blood pressure control^{4,7}. However, significantly more patients have side effects when taking nifedipine ER (48% versus 20%), and 24% of women using nifedipine ER report headache as a side effect⁷. Headache is a known symptom of preeclampsia, and its presence as a symptom can change patient management. When patients are using nifedipine ER, it can be difficult to determine if the headache is due to the medication or the disease, making management decisions difficult.

Like nifedipine ER, amlodipine is a dihydropyridine calcium channel blocker⁸. Headache is not a commonly reported side effect of amlodipine. Amlodipine is not commonly used in the postpartum setting, but a prior study in the non-obstetrical population demonstrated that amlodipine and nifedipine ER resulted in comparable reductions in blood pressure and can be considered equivalent. Amlodipine was also found to have a significantly lower rate of side effects than nifedipine ER (27% versus 41%)⁹.

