2.2 Secondary Objective

Secondary outcomes include the need for additional antihypertensive medications (either increased dose, additional long-acting agents, or additional short-acting agents), patient-

reported side effects, medication discontinuation due to side effects, hospital readmissions, duration of breastfeeding, and breastfeeding continuation and satisfaction.

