3 INVESTIGATIONAL PLAN

3.1 Study Design

This is an unmasked, pragmatic randomized controlled trial.

Women randomized to arm 1 will be started on amlodipine 2.5 mg daily. Women randomized to arm 2 will be started on nifedipine ER 30 mg daily. Dose adjustments will be made as deemed appropriate by the clinical team. Intravenous magnesium, additional long-acting antihypertensives, and short-acting antihypertensives will be administered as deemed appropriate by the clinical team. Women will be discharged from the hospital when the team feels that all discharge criteria have been met. While each provider may use slightly different discharge criteria based on their practice patterns, it is agreed upon that no patient will be discharged until her blood pressure is $< 160/110$ mmHg. They will be scheduled for a blood pressure check (virtual or in-person) ideally 3 to 7 days after discharge and an in-person visit ideally at 4 to 6 weeks postpartum. Participation in the study will not affect usual management aside from medication assignment.

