3.2 Allocation to Treatment Groups and Blinding (if applicable)

A computer-generated randomization schedule with 1:1 allocation will be utilized.

Randomization will occur at time of study enrollment utilizing REDCap. Randomization will be stratified by chronic hypertension diagnosis status. The research staff will be responsible for accessing the centralized randomization system, obtaining patient allocation, and notifying the treatment team of patient assignment.

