7 DATA COLLECTION AND MANAGEMENT

Data will be entered directly from the medical record into the REDCap data management system for storage and access for statistical analysis by the primary investigator.

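### Patient-reported side effects are taken from the medical record in an unmasked trial, with no common questions and no attribution rule, so headache could be recorded differently by arm

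*Combined protocol and SAP*

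**What the plan says.** Better tolerability of amlodipine is the only secondary objective in the Protocol Synopsis, and the end of section 1 predicts fewer side effects on that drug. Section 2.2 lists patient-"reported side effects, medication discontinuation due to side effects, hospital readmissions, duration of breastfeeding" among the secondary outcomes.

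On measurement, section 5 opens with a statement of chart abstraction and then gives one line, "Side effects reported". Section 7 states the data route: "Data will be entered directly from the medical record into the REDCap data management system". The synopsis (Follow-up) adds that side-effect data are gathered during the hospital stay and that further data are gathered at the two visits. Under Safety Evaluations it has the clinical team look for side effects daily.

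On masking, section 3.1 says "This is an unmasked, pragmatic randomized controlled trial", section 4.2 says randomization "will not be blinded", and section 3.2 makes research staff responsible for "notifying the treatment team of patient assignment".

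On headache, section 1 says that with nifedipine ER "it can be difficult to determine if the headache is due to the medication or the disease". The synopsis describes amlodipine as being in the same class "but does not cause headaches". Section 1 is milder and says only that headache is not commonly reported with it.

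**The concern.** A side effect is a symptom plus a judgement about its cause. The plan does not say who makes that judgement, by what rule, or whether every woman is asked the same questions. The team that looks for side effects knows the drug. For headache, the protocol admits that cause is hard to judge on one drug and, in the synopsis, rules the drug out as a cause on the other. An identical headache could thus enter the record as a drug effect in one arm and as preeclampsia in the other.

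Such an error would differ by arm and run in the direction of the hypothesis. The trial could then report better tolerability for amlodipine when symptom rates are equal, and nothing in the planned data would let a reader separate a drug effect from a labelling effect.

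**Working it through.** The documents give no calculation for this outcome and name no test for it, so there is no figure of the plan's own to reproduce. The check asks how much arm-dependent recording alone could do.

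**Inputs from the documents**
- Nifedipine ER, earlier postpartum trial (section 1): 24% headache, 48% any side effect.
- Arm sizes: 66 (section 6.1) and 80 (160 enrolled at 1:1, sections 3.2 and 3.3).

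**Assumptions, not in the documents**
- True headache is 24% in both arms.
- A share a₁ of headaches is recorded as a side effect under nifedipine ER and a share a₂ under amlodipine.
- The arms are compared by a two-sided test of two proportions at 0.05.

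**Formulas**
- Headache alone: p₁ = 0.24·a₁ and p₂ = 0.24·a₂.
- Any side effect: let q be the rate of non-headache effects, independent of headache and recorded equally in both arms. From 1 − (1 − 0.24)(1 − q) = 0.48, q = 1 − 0.52/0.76 = 0.316. Then pᵢ = 1 − (1 − 0.24·aᵢ)(1 − 0.316).
- z = (p₁ − p₂)/√[p₁(1 − p₁)/n + p₂(1 − p₂)/n], and P(p<0.05) = Φ(z − 1.96) + Φ(−z − 1.96).

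**Worked case, 80% v 50%, n = 66**
- Headache alone: p₁ = 0.192, p₂ = 0.120, SE = √[(0.1551 + 0.1056)/66] = 0.0629, z = 0.072/0.0629 = 1.15, P = 21%.
- Any side effect: p₁ = 0.447, p₂ = 0.398, SE = 0.0859, z = 0.57, P = 9%.

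**Results (66 to 80 per arm)**

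| Share recorded, nifedipine ER v amlodipine | Headache recorded | False p<0.05, headache alone | Any side effect recorded | False p<0.05, any side effect |
|---|---|---|---|---|
| 80% v 30% | 19.2% v 7.2% | 54–62% | 44.7% v 36.5% | 16–19% |
| 80% v 50% | 19.2% v 12.0% | 21–24% | 44.7% v 39.8% | 9–10% |
| 70% v 50% | 16.8% v 12.0% | 12–14% | 43.1% v 39.8% | about 7% |
| 80% v 70% | 19.2% v 16.8% | 6–7% | 44.7% v 43.1% | 5–6% |

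Equal shares return the nominal 5%. A large gap in recording matters, and a small one hardly does. The effect is diluted when headache is only one component of the outcome.

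**The case against.** The case against is substantial, and most of it limits the point rather than removing it.

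- **Clinician labelling is inferred.** A reader might take the plan to mean that a symptom counts only when a clinician who knows the drug labels it a side effect. No section says so. Section 2.2 calls the outcome patient-reported, section 5 says reported rather than attributed, and the same chart-headed list holds two breastfeeding items marked as patient-reported. The synopsis leaves room for direct collection, and the study-flow figure cannot be seen. This stands. What remains is that no method of asking and no rule on cause is described.
- **The mechanism is possible, not shown.** Nothing indicates that treating staff read the synopsis. The difficulty over headache is stated for nifedipine ER users only, and the asymmetry comes from pairing it with the synopsis line on amlodipine. The word is could, not will.
- **The larger figures describe an endpoint the plan does not name.** No headache outcome is listed, so 54–62% should not be read as the risk for the planned outcome. Under the same shares, any side effect gives 16–19%. That would rise if recording of other symptoms also differed by arm.
- **The 24% input is imperfect.** It is already a rate of headache reported as a side effect, so using it as the all-cause rate is a convenience. The recording shares are invented.
- **Pre-existing headache is balanced by randomization in expectation.** The lack of a pre-dose record mainly adds noise and is not a separate source of bias.
- **The design is pragmatic and the outcome secondary.** Both are true, and length of stay is not measured through side-effect attribution. But open treatment does not require open-ended symptom recording, and uniform questions need not alter care.

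**Conclusion.** The point holds as a gap in the plan: an outcome named as patient-reported has no stated way of being obtained from patients and no rule on attribution, in a trial where those who chart know the arm. The documents support a risk of error in favour of amlodipine. They do not show that it will occur, and they give nothing from which to estimate its size.

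Under the stated assumptions, a moderate recording gap (80% v 50%) raises the chance of a false difference from 5% to about 21–24% for headache alone and about 9–10% for any side effect. A wide gap (80% v 30%) gives 54–62% and 16–19%. These figures show sensitivity and are not predictions. A reader might infer that a tolerability advantage in this trial would be an artefact. The documents do not support that. They support only that the planned data could not rule it out. The primary noninferiority comparison is not affected by this point.

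**What to change.** Put one short symptom list, with headache on it, to women in both arms in the same words, daily in hospital and at the blood pressure check. Count any listed symptom present after the first study dose, whatever its presumed cause, and make this the side-effect outcome. Report chart-attributed side effects as supportive only.

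If no form can be added, the minimum is an abstraction rule: record all charted headaches and other listed symptoms after the first dose in both arms, regardless of attribution. A symptom record before the first dose is optional and must not delay treatment, since section 4.2 randomizes early to avoid delay.

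The cost is a short form and a few minutes of staff time at existing contacts. Disease symptoms will be counted in both arms, which dilutes any true drug difference. Some bias will remain, because women know their drug and, under the minimum version, charting stays unmasked. The change removes the attribution step but does not blind the outcome.

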6 STATISTICAL CONSIDERATION

6.1 Sample size calculation

An initial power calculation was performed using a standard deviation of 55.2 hours and a non-inferiority limit of 24 hours; to achieve 80% power with a 2-tailed alpha of 0.05, 66 women would be needed in each arm.

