Nifedipine ER is considered safe in breastfeeding women. Typically, a relative infant dose (RID) less than 10% is considered safe, and nifedipine ER has a RID of 2.3%. There is limited data on amlodipine use in breastfeeding women, and therefore the LactMed Database currently recommends an alternative to amlodipine if possible. However, one study has shown that the median RID for amlodipine is 4.18%, suggesting it is safe to use in breastfeeding women. In addition, multiple case reports of breastfeeding mothers using amlodipine did not demonstrate any adverse effects in the infant¹⁰. Although further data should continue to be collected, these prior studies and case reports are reassuring.

We hypothesize that amlodipine will be as effective as nifedipine ER in controlling blood pressures in patients with postpartum hypertension, as reflected by equivalent times from delivery to hospital discharge. In addition, we hypothesize that women taking amlodipine will report fewer side effects than those taking nifedipine ER. No effects on breastfeeding outcomes are expected.

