2 STUDY OBJECTIVE

2.1 Primary Objective

The primary hypothesis of this study is that amlodipine is noninferior to nifedipine ER in the management of postpartum hypertension, as evidenced by length of stay from delivery until hospital discharge. A noninferiority limit of 24 hours was selected as a clinically relevant difference.

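### With no true difference, 66 women per arm gives 80% power only at a one-sided alpha of 0.05; at the stated 2-tailed 0.05 it gives about 70%, and the planned 160 gives about 78%

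*Combined protocol and SAP*

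**What the plan says.** The sample size rests on one sentence in section 6.1 of the protocol. It describes an initial calculation made "using a standard deviation of 55.2 hours and a non-inferiority limit of 24 hours" and concludes that "to achieve 80% power with a 2-tailed alpha of 0.05, 66 women would be needed in each arm". Section 2.1 repeats the limit: "A noninferiority limit of 24 hours was selected as a clinically relevant difference". Section 6.1 gives no assumed true difference. The hypothesis in section 1 is that the drugs are equally effective, "as reflected by equivalent times from delivery to hospital discharge", so zero is the natural reading. Section 3.2 sets 1:1 allocation.

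Section 3.3 then says "160 patients will be enrolled", as does the synopsis. Nothing explains the step from 132 (2 × 66) to 160. The synopsis names the Wilcoxon rank-sum test for the primary comparison. No section gives a confidence level or a decision rule, and none mentions a one-sided alpha of 0.05 or a 90% interval.

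**The concern.** A noninferiority test looks in one direction only, so a 2-tailed alpha of 0.05 means a one-sided 0.025 and a decision on the upper limit of a two-sided 95% confidence interval. A common slip is to calculate with a one-sided 0.05 and report the result as 2-tailed 0.05. A size of 66 per arm looked too small for the stated inputs and about right for that slip.

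Two things are at stake. If the stated alpha governs, the trial falls short of its stated power. If the calculation governs, the trial was sized for a test with twice the risk of wrongly declaring noninferiority (5% rather than 2.5%). Because no other section fixes the confidence level, the two readings could give different primary conclusions from the same data, in an unmasked trial.

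**Working it through.** **Inputs**
- Standard deviation 55.2 h, limit 24 h, power 80%, 2-tailed alpha 0.05, 66 per arm: section 6.1.
- 1:1 allocation: section 3.2.
- Planned enrolment 160, that is 80 per arm: section 3.3.
- True difference 0 h: an assumption, in line with the hypothesis in section 1.

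**Sample size.** For a noninferiority comparison of two means,

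n per arm = 2 × (z_alpha + z_beta)² × SD² / limit², with SD²/limit² = (55.2/24)² = 2.3² = 5.29.

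- Reproducing the plan's figure, one-sided 0.05: 2 × (1.645 + 0.842)² × 5.29 = 65.41, so **66 per arm**. This is the stated number.
- At the stated alpha, 2-tailed 0.05: 2 × (1.960 + 0.842)² × 5.29 = 83.04, so **84 per arm** (168 in total).

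The t distribution gives 67 and 85 per arm. The gap of 84 − 66 = 18 per arm is too large to be rounding.

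**Power.** Power = Φ(24/SE − z_alpha), with SE = 55.2 × √(2/n).

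| Women per arm | SE (h) | 24/SE | Power, 2-tailed 0.05 | Power, one-sided 0.05 |
|---|---|---|---|---|
| 66 | 9.61 | 2.498 | 70.5% | 80.3% |
| 70 | 9.33 | 2.572 | 73.0% | 82.3% |
| 80 | 8.73 | 2.750 | 78.5% | 86.5% |
| 84 | 8.52 | 2.818 | 80.4% | 88.0% |

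At 2-tailed 0.05 the noncentral t distribution gives 69.8% for 66 per arm and 78.0% for 80 per arm.

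**What would rescue the stated pair.** At 2-tailed 0.05, 66 per arm reaches 80% power only if one of the inputs changes:
- The standard deviation is at most 24 / [(1.960 + 0.842) × √(2/66)] = 49.2 h; or
- amlodipine truly shortens the stay by about (1.960 + 0.842) × 9.61 − 24 = 2.9 h.

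The plan states neither.

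**Effect on the decision.** With 66 per arm, noninferiority needs an observed excess stay on amlodipine below:
- 24 − 1.960 × 9.61 = 5.2 h with a 95% interval;
- 24 − 1.645 × 9.61 = 8.2 h with a 90% interval.

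If the true difference is 0, the result falls between these two cut-offs in 80.3% − 70.5%, or about 10%, of trials. At 80 per arm the figure is 86.5% − 78.5% = 8%.

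**Wilcoxon test.** With normal data its efficiency relative to the t test is 3/π = 0.955, so 24/SE is multiplied by √0.955. Power at 2-tailed 0.05 is then about 68.5% with 66 per arm and 76.6% with 80.

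**The case against.** The strongest reply is that 70% is not the power of the planned trial. Section 6.1 calls its calculation initial, and the plan is to enrol 160. With all 160 analysed, power at the stated alpha is 78.5%, and a standard deviation of 54.2 h instead of 55.2 h would bring it to 80%. Losses may also be few, because delivery-to-discharge time is taken from the chart and does not depend on outpatient visits. This stands as a limit on the practical harm. It does not make section 6.1 correct: nothing presents 160 as a correction for alpha, 160 still falls short of 168, and any loss lowers power further (73.0% at 70 per arm).

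Second, the primary test is a rank test and length of stay is probably skewed. With gamma-shaped stays of the same standard deviation, simulated Wilcoxon power at 2-tailed 0.05 ranged from about 70% to 85% with 66 per arm, and from about 79% to 90% with 80, rising with the skewness. The normal-data Wilcoxon figures are therefore not a firm further loss. But the plan states no distribution, and its 66 is exactly what the formula for means gives at one-sided 0.05.

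Third, the documents state one alpha only, so the 90% interval is an inference from the arithmetic, and part of the uncertainty about the decision comes from the missing analysis rule. That is fair. The inference is still the simplest explanation of 66, and the only sentence that could settle the confidence level contradicts itself.

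**Conclusion.** Section 6.1 is wrong as written. From its own inputs, 80% power at a 2-tailed alpha of 0.05 needs 84 women per arm, and 66 per arm gives about 70%. The figure of 66 matches a one-sided alpha of 0.05. With the planned 160 all analysed, the shortfall is small, at 1.5 to 2 percentage points.

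These figures assume a true difference of 0, the stated standard deviation and a comparison of means. A true difference in favour of nifedipine ER would lower power further. That the calculation was run at one-sided 0.05 is likely but cannot be proved from the documents; that the stated alpha and size disagree does not depend on it.

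**What to change.** Correct section 6.1 so that alpha, sidedness, interval level, sample size and power agree, and state the assumed true difference. Either:

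- **Keep 2-tailed 0.05 (preferred).** Base the decision on the upper limit of the two-sided 95% confidence interval. State that 84 per arm gives 80% power, that 160 analysed women give about 78%, and that 132 give about 70%.
- **Declare a one-sided 0.05 test**, if that was intended. Say that the decision uses the upper limit of a two-sided 90% interval and that the risk of wrongly declaring noninferiority is 5%.

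With either choice, say how 132 became 160, write the same alpha and interval level into the primary analysis rule, and settle the choice before outcome data are seen. The cost is a change of wording and, under the first option, a slightly lower stated power. No extra patients are needed unless the sponsor wants the full 80% at 2-tailed 0.05, which takes 168 analysed women, 8 more than planned.
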